4.2. Secondary Outcome Measure

- Auxological parameters for each evaluation will include: length, weight, head circumference. They are routinely checked both during the baby's hospital stay and the routine follow-up clinics therefore we will not add any to the standard baby's care.
- External genitalia evaluation will include: testicular volume and position, penile length. This is not a part of the routine monitoring of preterm babies but it is not invasive and it will be done at the same time of plastic bag's positioning for urine collection in order to minimize handling of the baby.
- Short term neurocognitive outcome: during the hospital stay in the Neonatal Unit parents will be asked if they agree with video recording their baby using their mobile phone at home after discharge. We would like to assess the Fidgety Movements at 3 months of corrected gestational age using the Prechtl's method^{12,13}. If the parents agree, we will give an instruction sheet before they go home briefly explaining how they have to record their baby and for how long. Fidgety Movements are a spontaneous pattern of movements which parents can record without the need for a healthcare professional. Parents will upload their videos onto a secure video messaging system (www.vcreate.tv) which already has governance approval in GGC and is endorsed by the NHS. [name] is an Italian researcher at the University Hospital of Modena (Italy). She is a highly trained expert of Prechtl's Method and a member of the General Movements Trust. With an expert team she will review all the videos giving an evaluation of the Fidgety Movements pattern. We will

store the videos for a maximum of 10 years and will delete them after this time.

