3.5 Withdrawal of subjects

Participants have the right to withdraw from the study at any point for any reason.

4 Study Outcome Measures

Our study will include 3 types of different evaluations on each neonate:

- Multiple urine collections to evaluate urinary gonadotrophin levels
- Multiple clinical evaluations of auxological parameters and external genitalia
- Neurocognitive assessment at 3 months of corrected gestational age

Timing of sample analysis and simultaneously clinical evaluation will be as follow:

T1: 1-3 days of life

T2: 7 days of life

T2a – T2z: one per week until 40 weeks of post-conceptual age or until discharge from Neonatal Unit

T3-TX: urinary sample analysis and clinical evaluation during the routine follow up clinics until 12 months of corrected gestational age

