4.1 Primary Outcome Measure

Urine collection will be done with a plastic bag with a sticky strip on one end, made to fit over baby's genital area. In extremely preterm babies (<28 weeks of gestational age) urine collection will be from cotton wool in the nappy because of their sensitive skin.

Samples will be analyzed on fresh urine for urinary gonadotropin levels (FSH, LH) as detailed in laboratory tests section.

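### Nothing keeps an infant's earlier LH/FSH results from whoever measures the genitalia at later visits, so the secondary hormone-genitalia association could partly reflect expectation bias

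*Combined protocol and SAP*

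**What the plan says.** - **The outcome.** Section 2 lists a link between hormone levels and genital development as a secondary endpoint. Section 4.2 defines the readings: "External genitalia evaluation will include: testicular volume and position, penile length". It adds: "This is not a part of the routine monitoring of preterm babies but it is not invasive". The measurements therefore exist only because of the study.
- **Timing within a visit.** Of the genital examination, section 4.2 says "it will be done at the same time of plastic bag's positioning for urine collection". Section 4 also schedules sampling and clinical evaluation together at every time point.
- **Repetition.** Section 4 plans "Multiple clinical evaluations of auxological parameters and external genitalia". These take place at T1 (days 1-3), at T2 (day 7), then "one per week until 40 weeks of post-conceptual age or until discharge from Neonatal Unit", and after that as "urinary sample analysis and clinical evaluation during the routine follow up clinics until 12 months of corrected gestational age".
- **The assay.** Sections 4.1 and 4.3 have LH and FSH measured on fresh urine, in the hospital's own Biochemistry Department. Storage and batch assay after the last visit are not mentioned.
- **The analysis.** Section 6 uses Pearson correlation and then backward stepwise regression, at p < 0.05.
- **What is not stated.** No section gives an instrument, a technique or an examiner for the genital readings, an assay turnaround time, or a rule on who receives LH and FSH results and when.

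**The concern.** The two variables to be correlated are gathered in parallel over many months. One is a laboratory value that can become available while the study runs. The other is a bedside reading with no specified method. The Introduction also gives the expected direction: it links higher gonadotropins in premature boys to faster genital growth. An examiner who knows that an infant's earlier LH or FSH was high knows which reading would fit.

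Any shading in that direction would produce the association under test. Neither correlation nor stepwise regression can remove it afterwards, because the analysis sees only the recorded measurement. What is at stake is how one secondary result can be interpreted.

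**Working it through.** The plan gives no figure for this issue, so there is nothing to reproduce. Its sample size of 20 comes without power, effect size or SD, and is not disputed here. The check has two parts.

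**1. Which readings could be exposed?**

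- *T1:* no earlier hormone result exists, so it is not exposed.
- *The same-visit result at any visit:* the examination coincides with placing the bag, before that sample can be assayed, so it is not exposed. The bag sentence does not literally cover infants under 28 weeks, whose urine comes from cotton wool (section 4.1). Section 4 still pairs sampling and examination for them.
- *T2 and later:* at least one earlier sample has been taken, and the samples are assayed fresh. Its result could be known, and nothing prevents this.

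For scale, take an infant born at exactly 28 weeks who stays in the unit to 40 weeks, counting age as gestational plus postnatal. That is 40 − 28 = 12 weeks, so 12 examinations from day 7 onwards (T2 plus 11 weekly visits) before follow-up clinics. Each follows at least one earlier sample.

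**2. How large could the effect be?**

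Inputs from the documents: n = 20 (section 3.1) and p < 0.05 (section 6; two-sided assumed).

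Assumptions, none of them in the documents:
- one reading per infant at a single visit, all 20 infants available, normally distributed data, no true link;
- b = shift in the reading, in SD, per 1 SD of the earlier hormone result;
- ρ = correlation between the earlier hormone result and that of the current visit.

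Model, with H₀ the earlier result, H₁ the current one, Y the recorded reading, and e₁ and e₂ independent standard normal:

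H₁ = ρH₀ + √(1 − ρ²)·e₁

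Y = e₂ + bH₀

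Induced correlation of H₁ and Y = bρ/√(1 + b²)

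The critical Pearson correlation at 18 degrees of freedom is t/√(t² + 18), with t = 2.101. This gives 2.101/√(4.414 + 18) = 0.444.

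Examples of the induced correlation:
- b = 0.2, ρ = 0.3: 0.06/√1.04 = 0.059
- b = 0.3, ρ = 0.9: 0.27/√1.09 = 0.259

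Share of 40,000 simulated studies with p < 0.05 although there is no true link:

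| b | ρ = 0.3 | ρ = 0.5 | ρ = 0.7 | ρ = 0.9 |
|---|---|---|---|---|
| 0 (results withheld) | 4.8% | 5.1% | 5.2% | 5.2% |
| 0.2 | 5.6% | 7.0% | 8.8% | 11.4% |
| 0.3 | 6.4% | 9.0% | 13.6% | 19.6% |
| 0.5 | 8.7% | 15.8% | 27.1% | 43.5% |
| 0.7 | 11.2% | 23.7% | 43.5% | 67.4% |

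For b of 0.2 to 0.3 the range is 5.6% to 19.6%. Because the bias can act only through earlier results, it weakens as ρ falls. The rows for b = 0.5 and 0.7 show what stronger shading would do; nothing in the documents points to shading of that size, or of any size.

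**The case against.** The strongest reply is that the plan is silent, and silence is not exposure. No section says that the examiner receives the laboratory's output, or that results are reported during follow-up at all. Doing the examination while the urine is being collected is partial protection, since the paired result cannot yet exist. The readings may be made with an objective instrument that the protocol simply does not name. The study is preliminary, has 20 infants, and the affected link is secondary.

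Most of this stands, and it limits the point. A reader might infer that examiners do see the results, or that the readings are subjective. The documents support neither: they show only that access is not prevented and that the method is not specified. A reader might also extend the concern to the Fidgety Movements videos. Those are assessed by a separate expert team led from another hospital, and no defect is shown there.

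What does not stand is that the study's preliminary status makes the matter irrelevant. Section 6 sets a significance threshold, section 11 foresees journal publication, and the protection has to be in place before the readings are taken.

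**Conclusion.** The point holds as a possible bias, not a demonstrated one. Genital readings at T2 and later could be made with knowledge of earlier LH and FSH results, and the plan has no step against this. T1, the same-visit hormone result and the primary FSH/LH levels and timing are not exposed; the primary endpoints are assay values. A reader might infer that the study's main findings are compromised, but the documents do not support that.

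The size cannot be estimated from the documents. The 6% to 20% false-positive range, against 5%, rests on assumed shading of 0.2 to 0.3 SD per SD and an assumed between-visit hormone correlation of 0.3 to 0.9, for one correlation in 20 infants. It shows scale only. This is an inexpensive improvement to one secondary analysis and does not invalidate the study.

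**What to change.** Add to sections 4.2 and 4.3 that the laboratory holds each infant's LH and FSH results, or sends them only to a data file that genital examiners cannot open, until that infant's last genital examination, unless clinically required. Name the examiner role in the same place, so that it is clear to whom the restriction applies.

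The cost is one reporting instruction to the laboratory and restricted file access within the existing team. The access restriction is needed because the documents do not say whether those who examine the infants also keep the data. If they do, sending results to a shared file would mask nobody.

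One limit remains: examiners will still know gestational age. The measure therefore removes knowledge of the hormone results, but not every expectation about the infant.

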4.3 Laboratory Tests

Measurement of LH and FSH urinary levels will be made on fresh samples using electro-chemiluminescence immunoassay (ECLIA). Sample analysis will be performed by the Biochemistry Department of the Royal Hospital for Children in Glasgow using Abbott Architect i1600 instrument.

5. Assessment of Safety

We do not expect particular problems in this study. Urine collection will be made in the same way of routine collection in infants. Auxological evaluations are part of the routine care of preterm neonates and we will add a non-invasive evaluation of external genitalia without particular risks for the babies. Neurobehavioural development will be evaluated using parents' video only if they agree with video recording their baby. This will allow parents to stay at home without bringing their baby to the hospital.

6. Statistics and Data Analysis

Results shall be expressed as median (range) and analysed using Minitab. Some data may require log transformation. Pearson's correlation shall be used for univariate analysis of association of and multivariate analysis shall be performed using backward stepwise linear regression analysis including factors significant from univariate analysis (Pearson's correlation) as independent factors. The Mann Whitney U test shall be used for comparison of nonparametric data. Statistical significance shall be set at $p < 0.05$.

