2. Aim/Primary and Secondary Objectives

This is a preliminary prospective and crosssectional study aiming to describe “minipuberty” in male preterm children at the Royal Hospital for Children in Glasgow. The research project has been discussed by the Developmental Endocrinology Research Group at the University of Glasgow.

- **Primary Endpoint**

- To describe when urinary hormones (follicle stimulating hormone and luteinising hormone) start to raise and when they reach their peak among male preterm neonates born with a gestational age <32 weeks.
- To investigate if there is a difference in hormone levels and their peak timing between extremely preterm babies (<28 weeks of gestational age) and very preterm babies (28-32 weeks of gestational age).

- **Secondary endpoints**

- Identify a link between hormone levels and linear growth in the first months of life in preterm neonates.
- Identify a link between hormone levels and the development of external genitalia (testicular volume and position, penile length).
- Identify a link between hormone levels and short-term neurocognitive development.

3. Study Design

This is a preliminary prospective and cross-sectional study on male preterm children at the Royal Hospital for Children in Glasgow. The study will not include any investigational medical product. The research project has been discussed by the Developmental Endocrinology Research Group at the University of Glasgow.

This study will be performed according to the Research Governance Framework for Health and Community Care (Second edition, 2006).

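### The plan names only urinary FSH and LH, with no dilution marker, volume, timed collection or unit, so an apparent rise, peak or group difference could be urine dilution

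*Combined protocol and SAP*

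**What the plan says.** Section 2 sets two primary aims. The first is "To describe when urinary hormones (follicle stimulating hormone and luteinising hormone) start to raise and when they reach their peak". The second is "To investigate if there is a difference in hormone levels and their peak timing between extremely preterm babies (<28 weeks of gestational age" and those of 28-32 weeks.

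Section 4.1 describes the default collection: "Urine collection will be done with a plastic bag with a sticky strip on one end". Infants under 28 weeks have urine taken from cotton wool in the nappy instead. The section then refers onward: "Samples will be analyzed on fresh urine for urinary gonadotropin levels (FSH, LH) as detailed in laboratory tests section". Section 4.3 reads "Measurement of LH and FSH urinary levels will be made on fresh samples", gives the assay as ECLIA, names the laboratory and instrument, and stops there.

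Section 4 lists urine, clinical and neurocognitive evaluations; no blood hormone is measured. Urine is taken at days 1-3, at day 7, weekly until 40 weeks post-conceptual age or discharge, and then at routine clinics up to 12 months corrected age. Section 6 allows that some data may be log-transformed and assigns the Mann-Whitney test to nonparametric comparisons at the 0.05 level. No section mentions creatinine, specific gravity, osmolality, urine output or a unit for the hormone result.

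**The concern.** The level of a hormone in a urine sample depends on how much is excreted and on how much water it is excreted in. With neither volume nor a marker recorded, these two cannot be separated.

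- Dilution that varies at random between samples blurs onset and peak and costs power.
- Dilution that shifts with postnatal age, or differs between the two gestational-age groups, can create or hide exactly the effects that the study looks for.

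The secondary links to growth, genital development and neurocognition use the same values. The gap would be hard to repair later, because samples are assayed fresh and no storage is described.

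**Working it through.** **1. What the data can identify.** Write C for the measured level, E for excretion and V for urine flow.

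C = E / V, so log C = log E - log V.

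The change between two samples, or the difference between two groups, is Δlog C = Δlog E - Δlog V. Only C is observed. At constant excretion, halving the flow doubles C. A log transformation makes the dilution term additive but does not remove it.

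**2. Inputs.** The plan has no figure to reproduce: 20 infants are stated without a power calculation, a variance or a split between groups. Everything below is therefore assumed. Dilution is log-normal and independent between samples, with log-SD 0.5 (one SD is a factor of e^0.5 = 1.65). The test is a two-sided Mann-Whitney at 0.05.

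**3. False rise.** With constant excretion and 14 samples, the chance that some later sample is at least twice the first is 6%, 48% and 67% at dilution log-SD 0.2, 0.4 and 0.6.

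**4. Peak time.** The log level is height × exp(-(t - peak)² / (2 × width²)), the peak week is drawn from N(10, 2), other noise has log-SD 0.25, and the highest sample is taken as the peak (20,000 curves). Clinic intervals are assumed, because section 4 gives none. The table shows the chance of missing the true peak by more than 3 weeks.

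| Sampling | Height (log units), width (weeks) | No dilution | Log-SD 0.5 | Rise (points) |
|---|---|---|---|---|
| Weekly, weeks 1-20 | 1.6, 5 | 5% | 22% | 17 |
| Born at 26 wk, weekly to 40, then 8-weekly | 2, 4 | 1% | 8% | 7 |
| Born at 30 wk, weekly to 40, then 8-weekly | 1.6, 5 | 16% | 32% | 16 |
| Born at 30 wk, weekly to 36, then 4-weekly | 2, 4 | 4% | 23% | 20 |
| Born at 30 wk, weekly to 36, then 4-weekly | 1.6, 5 | 15% | 41% | 26 |
| Born at 30 wk, weekly to 36, then 8-weekly | 2, 4 | 42% | 55% | 12 |

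Rises are taken before rounding. Over 16 combinations of schedule and curve the rise ran from 7 to 26 points, and about half fell between 14 and 24.

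**5. Power.** Take 8 v 12 infants, a true difference of 0.9 log units and a between-infant SD of 0.6.

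- One sample per infant: the SD goes from 0.6 to √(0.6² + 0.5²) = √0.61 = 0.78. Simulated power goes from 85% to 63%, a loss of 22 points (20 if other noise of 0.25 is added).
- Median of 5 to 8 samples, other noise 0.25: power goes from about 82-84% to 75-80%, a loss of 4 to 8 points.

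**6. False group difference.** Use the same set-up with no true difference and a systematic dilution ratio between the groups. Share of studies with p<0.05:

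| Dilution ratio | One sample | Median of six |
|---|---|---|
| 1.0 | about 5% | about 5% |
| 1.22 | 7-8% | 9-10% |
| 1.5 | 16-18% | 23-24% |
| 2.0 | 39-42% | 56-57% |

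Repeated samples make this worse: they average out random noise and leave the systematic shift. The rate also depends on the total spread. With 10 v 10 infants, ratios of 1.5 and 2 give 34% and 79% at a total log-SD of 0.5, and 17% and 41% at 0.8.

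**The case against.** Several stronger readings are tempting, and the documents do not support them.

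- *That the plan uses raw concentrations in spot urine.* The plan speaks only of urinary levels and gives no unit. The laboratory might normalise in practice. What can be said is that the plan does not specify it, and this is enough for the point to stand.
- *That power falls by more than 20 points.* This needs one urine value per infant. Section 4 plans many, and with a per-infant median the loss is about 5 points. Section 6 does not define the per-infant summary, which is a separate gap.
- *That dilution is the main source of error in peak time.* Weekly sampling stops at 40 weeks or discharge. For an infant discharged at 36 weeks and then seen every 8 weeks, the peak is missed by more than 3 weeks in 42% of cases with no dilution noise at all. Dilution still added to the error under every schedule tried.
- *That dilution does differ between the groups.* Nothing in the documents shows this. The rates in step 6 are conditional on an assumed ratio and are small at 1.22-fold.
- *That the creatinine ratio should be the main analysis.* Creatinine may change with maturity, which is the axis of both primary questions, so the ratio could create or hide the same effects. This objection stands in full against imposing the ratio. It does not justify leaving dilution unmeasured.

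It can also be said that the study is preliminary. It nevertheless compares groups at the 0.05 level with 20 infants, so an uninterpretable difference matters.

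**Conclusion.** The point holds as an omission. Followed as written, the plan cannot separate hormone output from urine dilution in the onset, the peak level, the peak time or the group comparison.

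The algebra in step 1 needs no assumed values; the sizes do. At dilution log-SD 0.5 the power loss is modest with repeated samples (about 5 points) and larger with one (about 20). The loss of accuracy in peak time is material but depends on the schedule and the curve. The more serious risk is a systematic shift, because more samples do not reduce it: 16-56% false differences at 1.5- to 2-fold, and 7-10% at 1.22-fold. Whether such a shift exists cannot be learned from the documents, or from the data as planned. A reader should not conclude that the results would be wrong, only that their cause could not be established.

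**What to change.** - **Section 4.3:** measure a dilution marker (creatinine, specific gravity or osmolality) on the same urine at every sample from T1 to TX where volume allows, and state the reporting units.
- **Section 6:** pre-specify that onset, peak level, peak time and the group comparison are reported both uncorrected and dilution-adjusted on the log scale. Show the marker itself by age and by gestational-age group. Treat as robust only conclusions that hold in both forms.

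The cost is one extra assay per sample, on urine already collected. Cotton wool may yield too little volume for some samples, and discordant results would have to be explained. A marker does not solve a separate problem in section 4.1: cotton wool is used for infants under 28 weeks and bags for the rest, so collection method is confounded with the group comparison whatever is done about dilution.

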Statistical Analysis:	Results shall be expressed as median (range) and analysed using Minitab. Some data may require log transformation. Pearson's correlation shall be used for univariate analysis of association of and multivariate analysis shall be performed using backward stepwise linear regression analysis including factors significant from univariate analysis (Pearson's

	correlation) as independent factors. The Mann Whitney U test shall be used for comparison of nonparametric data. Statistical significance shall be set at $p < 0.05$.
--	--

Full title: PRELIMINARY STUDY ON ACTIVATION OF THE HYPOTHALAMIC-PITUITARY-GONADAL AXIS IN INFANCY (MINIPUBERTY) AND ITS EFFECTS ON CATCH-UP GROWTH AND NEUROCOGNITIVE OUTCOME IN MALE PRETERM NEONATES BORN AT <32 WEEKS OF GESTATIONAL AGE

Short title: Minipuberty and its effects on preterm neonates

1. Introduction

The activation of the hypothalamic-pituitary-gonadal axis (HPG) develops through three main moments: foetal life, first postnatal months (usually first 6 months of life) and finally during puberty.¹ During the foetal period, there is a peak of gonadotropin secretion starting from the second trimester of gestation, and a subsequent suppression in the last weeks until birth, due to the negative feedback of placental estrogens.² In male foetuses, LH levels exceed those of FSH. The foetal testis secretes testosterone and anti-müllerian hormone (AMH) from the 8th week of gestation and this is essential for masculinization. Formation of the active metabolite of testosterone, dihydrotestosterone, is required for the development of the prostate, penis and scrotum.³ Initial testicular development is intra-abdominal and the descent of the testes into the scrotum occurs in two phases. The first, transabdominal, phase is completed by 15 weeks of gestation. The second, inguinoscrotal, phase is usually completed by the end of the 35th week of gestation and this phase is androgen dependent. Testosterone levels are high in male foetuses between 10 and 20 weeks of gestational age, reaching adult values, and decrease thereafter towards term.⁴ In the same way LH and FSH levels decrease towards the end of gestation and are low at term in both sexes, due to the negative feedback of placental oestrogens.

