A second post-natal HPG activation, also called "minipuberty", occurs at around 1 week of age, when placental hormones are cleared from the circulation. From the first weeks of life onwards there is a progressive increase in gonadotropins levels with a greater increase of FSH in females and of LH in males. During the "minipuberty" period gonadotropins levels have a peak at 3 months of life and a progressive exhaustion at around 6 months, except for FSH levels in females that can remain high even up to 3 or 4 years. Particularly in males, testosterone and androgen levels are associated with development and maturation of the reproductive system (penis and testis) as well as the androgynous cutaneous manifestations and a different neurobehavioral structure.⁵ Postnatal testosterone levels have been associated with male-type behaviour in 14-month-old infants, suggesting a role in neurobehavioral development.⁶ Recently, it has also been suggested how the increasing testosterone level during the first 6 months of life, as well as during puberty, translates into an increase of linear growth, regardless of the levels of growth hormone (GH) or insulin-like growth factor (IGF1).⁷ Preterm birth does not seem to influence post-natal HPG activation, since that gonadotropin levels seem to raise up at the same time as term infants after the birth. The difference is that in preterm neonates these values last higher and longer than full-term newborns. According to the most recent longitudinal data, the post-natal activity of this axis declines at about the same in term neonates compared to premature infants with the same corrected gestational age, suggesting that the HPG activity is evolutionarily regulated.^{8,9} This higher increase of gonadotropin levels in premature males has been associated with a faster penile and testicular growth after birth compared to full-term boys. At last, in neonates small for gestational age (SGA) there are some evidence that post-natal FSH and testosterone levels are higher compared to infants with an adequate weight (AGA), although it is not known

whether this correlates or have any influence on the catch-up growth of this subjects.^{10,11} Understanding how “minipuberty” can influence linear growth, genitalia development and neurocognitive processes in preterm neonates has a significant scientific impact and could provide us more information in understanding auxological and neurobehavioral developmental patterns of this population.

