3.1 Study Population

We aim to enroll 20 neonates born under 32 weeks of gestational age at the Royal Hospital for Children in Glasgow. Neonates will be enrolled during the first 3 days of life with written informed consent signed by their parents.

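### Section 6 selects factors by Pearson significance and backward stepwise regression in 20 infants, so the p-values and coefficients of the surviving factors ignore how they were chosen

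*Combined protocol and SAP*

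**What the plan says.** The statistical plan is one paragraph, in Section 6 (Statistics and Data Analysis) and again in the synopsis under Statistical Analysis. On associations it names Pearson's correlation for the univariate step and then says that "multivariate analysis shall be performed using backward stepwise linear regression analysis including factors significant from univariate analysis", the univariate test being that correlation. Significance is p<0.05; no separate removal threshold is given. In both copies the sentence breaks off after the words introducing the association ("Pearson's correlation shall be used for univariate analysis of association of and multivariate analysis shall be performed using backward stepwise linear regression analysis"), so the variables it was meant to name cannot be read.

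Section 3.1 sets the size: "We aim to enroll 20 neonates born under 32 weeks of gestational age". The objectives that call for association analysis are the secondary ones in Section 2, for example "Identify a link between hormone levels and linear growth in the first months of life in preterm neonates", with parallel objectives for external genitalia and short-term neurocognitive development. Results are to be summarised as median and range. No fixed model, forced covariate, shrinkage, resampling or multiplicity correction appears, and these results are not labelled exploratory, although the study as a whole is called preliminary.

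**The concern.** A factor reaches the multivariate model only if its correlation in these 20 infants is large enough to be significant, and stays only if it is significant again. Ordinary regression output treats the final model as if it had been fixed in advance. Its p-values are therefore too optimistic, and retained coefficients are biased away from zero because smaller estimates of the same effect were discarded. A covariate that matters can also be dropped simply because 20 infants are too few to show it. Gestational age is the obvious case, since the second primary objective is built on it.

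At stake are the links of LH and FSH with linear growth and genital size. A preliminary study is often used to plan the next one, and effect sizes that come out nearly double would mislead that planning.

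**Working it through.** The documents give no power, effect size or standard deviation, so there is no stated figure to reproduce.

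**Inputs from the plan.** n = 20 (Section 3.1); p<0.05, Pearson screen, then backward elimination (Section 6).

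**Assumed.** Two-sided tests, removal at 0.05, one value per infant, normal data, and the candidate numbers and effect sizes shown below. With five independent null candidates, removal at 0.10 instead of 0.05 left the chance of a false factor at 22%.

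**Step 1: what passes the screen.** With 18 degrees of freedom t = 2.101, so the critical correlation is t/√(18 + t²) = 2.101/√22.414 = 0.444.

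**Step 2: chance of passing.** By Fisher's z, the chance of failing is about Φ{(atanh 0.444 − atanh r)·√17}.
- r = 0.3: Φ{(0.477 − 0.310) × 4.123} = Φ(0.69), or 75% fail and 25% pass. Simulation also gives 25%, and the correlations that pass average 0.55.
- r = 0.4: Φ{(0.477 − 0.424) × 4.123} = Φ(0.22), or 59% fail. Simulation, which avoids the approximation, gives 57%.

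**Step 3: the written rule, simulated.** Five independent candidates, one with a true effect, 8,000 runs per row:

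| True standardised slope | Mean when kept | Ratio | Coverage of a nominal 95% interval |
|---|---|---|---|
| 0.2 | 0.53 | 2.6 | 78% |
| 0.3 | 0.55 | 1.8 | 90% |
| 0.5 | 0.61 | 1.2 | 96% |
| 0.7 | 0.71 | 1.0 | 96% |

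**Step 4: a version closer to this study.** Candidates are LH (true effect 0.3), FSH (correlated 0.5 with LH, no effect of its own) and gestational age (correlated 0.4 with growth, uncorrelated with the hormones). LH is kept in 21% of studies. When kept, its coefficient averages about 0.54, a 95% interval covers the truth 88% of the time, and gestational age is absent from 73% of those models. A fixed model of LH with gestational age gives a mean of 0.30 and 95% coverage.

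**Step 5: false hormone links through gestational age.** If the hormones have no effect but correlate 0.5 or 0.7 with gestational age, the rule reports a hormone link in 12% or 17% of studies. The fixed model gives 9-10% over the same two tests.

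**Step 6: what is not selection.** With no true association, the rule keeps at least one factor in 10/18/26/39% of studies for 2/4/6/10 independent candidates. The chance of any significant result among k independent tests is 1 − 0.95^k = 10/19/26/40%. The two agree, so these figures measure the number of tests, not the stepwise step.

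**The case against.** The strongest reply is that the study is preliminary, the objectives are secondary, and they are worded as looking for a link. Section 6 also plans the Pearson correlations themselves and does not say that non-significant ones will be withheld; if all were reported, the univariate results would not be inflated. Both points stand and lower the stakes. Neither corrects the coefficients and p-values of the multivariate model, which by its own rule contains only selected factors.

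It is also fair that the harm in false links is modest (12-17% against 9-10%) and that every magnitude rests on assumed effects. The main damage is the inflation of weak to moderate coefficients.

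A reader might infer more than the documents support:
- **That 10-39% measures the harm of stepwise selection.** It is multiplicity, and a fixed model would not remove it.
- **That the plan fails to name its variables.** The sentence is cut in both copies and the list may have been lost there.
- **That gestational age will be dropped.** This holds only if it is a candidate, and the rate depends on the assumed correlation.
- **That misleading confidence intervals are promised.** None is mentioned; the interval point applies only if they are reported.
- **That serial samples will be pooled as independent.** Section 4 schedules repeated samples, "one per week until 40 weeks of post-conceptual age or until discharge from Neonatal Unit", but pooling is neither stated nor excluded.

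**Conclusion.** The concern holds for the p-values and coefficients of the factors that survive selection. The critical correlation of 0.444 follows from the plan's own n and significance level. The rest is conditional: an assumed effect of 0.3 is reported at about 0.55 when kept, and an assumed gestational-age correlation of 0.4 fails the screen in about 57% of studies. By a true correlation of 0.7 the inflation has almost gone, but 20 infants cannot show in advance which case applies.

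Applying the rule to the secondary links is an inference, though a sound one, because those are the association objectives. The primary aims (timing of the rise and peak, and the comparison of the two gestational-age groups) do not depend on it. This should be fixed, but it does not threaten the study's main purpose.

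**What to change.** Replace the association sentences in Section 6 and the synopsis with:

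> No univariate screening or stepwise selection is used. The unit of analysis is the infant. For each continuous secondary outcome (linear growth, change in penile length, change in testicular volume), one linear regression per hormone relates a pre-specified per-infant summary of log LH or log FSH to the outcome over the same pre-specified age window, adjusted for gestational age at birth. The same model with birth-weight z-score added is reported beside it, and both are interpreted together. Fidgety Movements and testicular position, if recorded as categories, are compared by hormone level with the Mann Whitney U test (Kruskal-Wallis if there are more than two categories). All estimates are reported with 95% CIs, significant or not; secondary p-values are labelled exploratory and the number of tests is stated.

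The categorical provision is needed because the video review consists of "giving an evaluation of the Fidgety Movements pattern", which may not yield a continuous score. The Mann Whitney test is already in the plan.

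Both models are shown because the Introduction reports some evidence of higher FSH in small-for-gestational-age infants, while saying that any influence on catch-up growth is unknown. If birth size correlates 0.3/0.5/0.7 (assumed) with both hormone and growth, the model with gestational age alone gives a false link in 7/18/59% of tests, against 5% with birth size added. At 0.5, over both hormones, gestational age alone gives 28-31%. That is worse than the present rule if offered birth size (10-13%); with both covariates it is 9%. The gestational-age-only result should therefore not be read by itself. A rule that suppresses any link seen only without birth size is not advised. With a true effect of 0.4 and birth size correlated 0.5 with the hormone and having an effect of 0.3 on growth (all assumed), it cuts detection from 71% to 39%.

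**Cost.** Wording only, using the same data plus birth weight. Fewer factors will be called significant, intervals will be wider, and power reaches 80% only for a correlation of about 0.58. Multiplicity remains: three outcomes by two hormones make six tests, and at least one falls below 0.05 in 16-27% of null studies, depending on how correlated the tests are.

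The team must also choose the summary and the window. The Introduction says that "gonadotropins levels have a peak at 3 months of life and a progressive exhaustion at around 6 months", whereas weekly sampling stops at 40 weeks post-conceptual age or at discharge. For an infant born at 31 weeks that is at most 40 − 31 = 9 weeks of age, so covering the peak depends on clinic samples.
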